Appendix B. Sample Care Plan

This patient is part of the ED-LINC (Emergency Department Longitudinal Integration and Coordination) Pilot Program at Harborview Medical Center. If you have any questions or if we can be of any help, please call or text the 24/7 program cell phone at [contact]

1. Please provide patient with clinic phone number, provider name and instruct them to contact their provider's office for follow-up visit as needed

- Provider Name:
- Clinic Name:
- Clinic Phone Number:

Updated xx/xx/yyyy (insert date)

Appendix C. ED-LINC PATIENT SAFETY SUICIDALITY PROTOCOL

This protocol addresses potential subject suicidal risk given that suicidal ideation is common among the patient population. Suicidal risk is indicated by subject self-report of suicidality or suicidal behavior. The following procedure addresses positive responses to the PHQ-9 or other reports of suicidality by study patients. Importantly, patients with a primary chief complaint of suicidal ideation or in the ED for treatment after a suicide attempt are not eligible for participation.

The study team collects patient-reported outcomes at baseline, prior to randomization, and at a series of post-randomization follow-up assessments according to a pre-determined schedule (1, 3, 6 months after the baseline assessment). These assessments include questions about patient psychological and emotional distress. Each assessment includes a question about having thoughts of self-harm or being better off dead on the Patient Health Questionnaire 9 item (PHQ-9) depression measure. The PHQ-9 question #9 asks patients “how often have you been bothered by thoughts that you would be better off dead or of hurting yourself in some way?” The response choices are: 0 = Not at all, 1 = A little of the time, 2 = More than half the time, 3 = Nearly all the time.

Work by Gregory Simon et al. (2013) in a general medical setting documented a low risk of completed and attempted suicide by subjects that endorsed a “1” on the PHQ-9 item #9 question; of those that responded with a “1”, approximately 1% attempted suicide and 0.08% completed suicide. The rates of attempts and completed suicide did increase with higher scores on the PHQ-9 item #9; however, the absolute risk remained relatively low; of those that endorsed a “3” on the PHQ-9 item #9, 4% attempted suicide over the course of a year. The low risk of suicide completion associated with a positive PHQ-9 led the study team to include a follow-up question to directly assess whether patients are currently having thoughts of suicide.

Suicidality or suicidal behavior discovered at baseline

If a patient indicates anything greater than 0, “Not at all,” on PHQ-9 item #9, the interviewer will ask a Yes/No follow-up question, labeled #9a *“Over the past two weeks, have you had any plans to harm yourself or take your own life?”* (or “in the past month” for follow-up interviews). If the patient endorsed a “Yes” to item 9a, following completion of the assessment (or earlier if needed), the interviewer will provide the patient with a suicide crisis line and call the study’s 24/7 cell phone after the assessment to inform the study clinical team about the patient. A member of the clinical team will assess the patient either in person at the hospital or via phone to assess risk and safety plan. If there is imminent danger of self-harm the interviewer or member of the study team will inform the participant of the need to inform hospital staff. Of note, if during the baseline interview or during the initial follow-up by the study team to baseline interview responses the study team learns that the subject’s initial injury was due to a suicide attempt, the subject will be withdrawn by the study team per the exclusion criteria. If the study team learns that the initial injury was due to a suicide attempt at any other point during the subject’s trial participation, the subject will be eligible to continue study participation.

If the patient reports a “No” to item 9a, but is otherwise positive on PHQ-9 item #9, the interviewer will provide the patient with a suicide crisis line (see below). A member of the clinical team will visit the patient in the hospital to assess risk and discuss suitable safety planning.

Should the patient inform the interviewer that they have current suicidal ideation and intent outside of the interview questions; the interviewer will inform hospital staff. If the patient

indicates they are having suicidal thoughts at any other time during the baseline assessment, even if the response to the PHQ-9 item 9 is 0, the recruiter will inform the clinical team following completion of the baseline assessment who will, in turn, follow the aforementioned procedures according to randomization assignment.

Suicidality or suicidal behavior discovered at follow-up

The following protocol is initiated if a subject indicates anything greater than 0, “Not at all,” on PHQ-9 item #9.

If the participant indicates a response > 0 on the PHQ-9 item #9, the subject will be asked the follow-up question, item #9a: “Do you currently have thoughts of killing yourself or ending your life?”

If 9a = Yes

If the subject responds “yes” to item #9a, (“*Over the past two weeks (or “month” at follow ups), have you had any plans to harm yourself or take your own life?*”) the study team member will conduct a warm hand-off with the subject to a member of the study clinical team (e.g., physician or MSW). The subject will also be provided with a crisis line number.

*If subject endorses a “Yes” on item #9a and he/she refuses a warm hand-off to the clinical team, the follow-up interviewer will let the subject know they will be contacted by our clinical team to follow-up. The interviewer will provide the subject with a crisis line number and immediately notify the clinical team at the 24/7 study cell.

- A clinical team member will attempt to call the subject within 24 hours and assess the patient’s suicide risk and determine the appropriate action (e.g., develop a safety plan; help patient obtain emergency services).
- If the subject is in the intervention, the subject’s suicidality will be addressed ongoing as part of the ED-LINC intervention.

If 9a = No, 9 = 3

If the subject responds “no” to item #9a and responded as a “3” to item #9, the study team member will provide the subject with a crisis line number and inform the subject that the clinical team will follow up with the subject over the phone in the coming weeks. The study team will add the subject to a list for the clinical team to call and assess risk and discuss suitable safety planning. The clinical team will regularly set aside time (e.g., weekly) to call subjects from the list. It may take the team more than one week to reach any given subject.

If 9a = No, 9 = 2 or 1

If the subject responds “no” to item #9a and endorses a “1” or “2” to item #9, the study team member will provide the subject a crisis line number.

For all subjects that endorse a positive response to PHQ-9 item #9, the study team will:

- Provide a crisis line number in the payment letter with their check.
- Additionally, crisis line numbers may be texted, emailed, or sent via private social media messaging, at subject’s request or approval.
- Inform study clinical team (via electronic log, email, in person, phone, etc.) so they can review that procedures have been properly adhered to and address any remaining safety concerns.

Should the subject inform the follow-up interviewer that they are having suicidal thoughts at any other time during the assessment, even if the response to the PHQ-9 item 9 is 0, the interviewer will inform the clinical team to assess the subject's need for further suicide risk intervention.

There are other ways that the research study team members who conduct follow-up assessments with subjects may become aware of suicidal ideation or behavior besides during a study assessment. For instance, a study team member may be told by a subject while contacting the subject to schedule a study assessment that the subject is suicidal or having thoughts of taking his/her own life. In this case, the study team member will follow the protocol for a 9a = Yes above (i.e., warm handoff to the clinical team).

A study team member may find out that a subject has attempted suicide or died by suicide during attempts to find and contact a subject through a public records search (e.g., WA state death records), from public posts or private messages sent through the subject's social media (e.g., Facebook), or even relayed by an alternate point of contact for the subject. In this case, research study team members will notify the clinical team, who will address any patient safety concerns.

Suicidality or Suicidal Behavior Discovered During Study Intervention Delivery

Intervention team members interacting with subjects, such as the social worker or peer interventionists, may become aware of subject suicidality, such as through care management phone calls or other intervention-related activities, assessing symptoms, or when viewing the subject's medical record. If a non-clinical team member becomes aware of subject suicidality they will inform the clinical team members via the 24/7 study cell, so that they can assess suicidality severity and make decisions about how to address patient safety concerns for those subjects deemed to be at risk for suicide. The intervention team will address suicidality as it occurs as a normative part of the ED-LINC intervention. Actions may include additional assessment regarding a subject's suicidal ideation, plan, means, intent and history of attempts, discussion of subject's suicidality and overall recovery during weekly case reviews, safety planning, and referrals to treatment if deemed necessary.

Tracking and Reporting of Subject Suicidality

Adherence to this protocol and patient suicidality concerns will be tracked; however, this will not be reported to the DSMB unless it reaches the level of an SAE (i.e., suicide attempt, hospitalization due to suicidal ideation or attempt, or death).

Suicide Prevention Resources

- Crisis Connections**

24 hour, toll-free, telephone hotline provides immediate, confidential assistance to people in distress in the King County area. Call [name] ([name]) or [contact].

- National Suicide Prevention Lifeline**

Provides 24 hour, toll-free, telephone support for anyone in suicidal crisis or emotional distress and provides information to locate crisis clinics and resources throughout the U.S. [name]

- **Veterans Crisis Line**

Veterans and family members can receive confidential help by calling [name] (then PRESS 1). Visit online to access confidential online chat help.

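### Appendix C words follow-up suicidality item 9a both as current thoughts and as recent plans, leaving the safety response undetermined for participants with only one of the two

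*Protocol*

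**What the plan says.** All of the triage text is in Protocol Appendix C. Its introduction explains that a further question was added after PHQ-9 item 9 to find out directly whether the participant has suicidal thoughts now.

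The baseline section words that question, 9a, as plans over two weeks, and changes the window ("or “in the past month” for follow-up interviews").

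The follow-up section has anyone scoring above 0 on item 9 asked 9a, given there as "Do you currently have thoughts of killing yourself or ending your life". Under the next sub-heading, for a Yes to 9a, the same item is given as "have you had any plans to harm yourself or take your own life".

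The responses at follow-up are:

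- **9a Yes:** "the study team member will conduct a warm hand-off with the subject to a member of the study clinical team", plus a crisis-line number. If the hand-off is refused, the clinical team is notified at once and "A clinical team member will attempt to call the subject within 24 hours".
- **9a No, item 9 = 3:** a crisis-line number and a place on a list for the clinical team to call. "It may take the team more than one week to reach any given subject".
- **9a No, item 9 = 1 or 2:** "the study team member will provide the subject a crisis line number".

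**The concern.** One item label carries two questions that differ in content (thoughts against plans) and in time (now against the past month). The answer to 9a alone decides whether a participant positive on item 9 is passed directly to a clinician. A person can truthfully answer Yes to one question and No to the other, and an interviewer or form designer working from Appendix C cannot tell which answer should count. What is at stake is the speed and kind of clinical contact for people who have just reported thoughts of being better off dead or of self-harm.

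**Working it through.** No formula applies to the rule itself, so the check sets the texts side by side and traces each branch.

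**Which wording does each part of Appendix C support?**

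| Place in Appendix C | Supports |
|---|---|
| Introduction, purpose of the added question | current thoughts |
| Baseline section, 9a with its follow-up window | recent plans |
| Follow-up section, where 9a is introduced | current thoughts |
| Follow-up section, Yes branch | recent plans |
| Follow-up section, suicidality disclosed while scheduling (handled as 9a = Yes) | current thoughts |

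Of the three places that actually word 9a, two use plans and one uses thoughts. The stated purpose and the scheduling rule favor thoughts. No sentence gives either precedence or says that both are asked.

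**What follows for a participant positive on item 9 at follow-up?**

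| Participant | 9a as thoughts | 9a as plans |
|---|---|---|
| Current thoughts, no recent plan | Yes: warm hand-off | No: lower tier |
| Recent plan, no current thoughts | No: lower tier | Yes: warm hand-off |
| Both | Yes: warm hand-off | Yes: warm hand-off |
| Neither | No: lower tier | No: lower tier |

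The lower tier is a crisis-line number if item 9 is 1 or 2, and a crisis-line number plus the call list if it is 3. The wordings diverge for exactly two kinds of participant. The rule applies at the 1-, 3- and 6-month assessments.

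**How many people?** The documents do not give the share with thoughts only or a plan only, so the number affected cannot be derived. The Protocol (Section V.A, AE and SAE Identification) reports that in prior work as many as 50% endorsed item-9-type thoughts over six months. Assuming that figure carries over, those reaching 9a would number at most:

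- 0.50 × 60 = 30, with the Protocol's planned sample;
- 0.50 × 40 = 20, with the SAP's 20 + 20.

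Those affected are an unknown part of that group, anywhere from none to all of it.

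**Do the safeguards close the gap?**

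- Appendix C has the clinical team informed of every positive item 9, to check adherence and deal with remaining concerns. It sets no deadline and requires no contact.
- Suicidal thoughts voiced elsewhere in the assessment go to the clinical team. This depends on disclosure and does not mention a past plan.
- Suicidality noticed during intervention delivery is escalated, but only the intervention arm has such contacts.
- Section V.A has the PI review anticipated suicidality events within 24 hours of discovery, and Section VII.B.2 feeds patient-reported suicide items into that log. The stated purpose is to decide whether the event is an unanticipated problem, not to reach the participant. The listed event could also be read as covering only attempts and deaths.

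Together these soften the gap without closing it.

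**The case against.** The strongest reply is that this is a drafting leftover. Two of the three statements of 9a use plans, both with a window set for follow-up, so the forms may have carried that one question throughout and every participant may have been routed alike. That stands as far as care delivered is concerned. It does not repair the text, because the introduction and the scheduling rule point the other way.

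A second reply is that the 24-hour PI review already catches these participants. It is the nearest timed safeguard and deserves weight, but it is a reporting check and not a clinical contact.

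A third is that any single question leaves out someone, so asking for two is a preference. That is fair: choosing one item is a design decision, and the inconsistency itself is cured by settling on either wording. The two-question version is offered as the better fix, not as a requirement.

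A reader might go further in three ways that the documents do not support:

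- **That participants received different care.** The interview forms are not available, so this is not shown.
- **That self-completed follow-ups make the problem worse.** The Follow-up Interviews section permits self-completion when scheduling is difficult, but nothing says how 9a is handled on such a form.
- **That the two recall periods also conflict.** Two weeks at baseline and one month at follow-up is a clear distinction and can stay.

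**Conclusion.** The inconsistency holds as a fault in the current text of the follow-up triage rule. For a participant positive on item 9 with only thoughts or only a plan, Appendix C yields a warm hand-off under one wording and a lower tier of response under the other, and does not say which applies. Confidence is high for the mismatch and its routing consequence on paper. No claim is made about care delivered, and the 50% figure at most bounds those reaching 9a.

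The baseline effect is small. Only the plans wording appears there, and a No from a participant positive on item 9 still brings clinical contact: "A member of the clinical team will visit the patient in the hospital to assess risk and discuss suitable safety planning". No outcome, randomization or analysis depends on 9a. Severity is minor to should-fix: the scope is narrow, but the rule governs participant safety and is cheap to correct.

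**What to change.** **Minimum:** choose one follow-up wording of 9a and use it in the baseline section's follow-up parenthesis, in both places in the follow-up section, and in every follow-up form.

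**Preferred:** at follow-up, ask everyone positive on item 9 about current thoughts of suicide and about plans in the past month, as 9a and 9b, with Yes to either triggering the warm hand-off. One combined item would also work, but would not tell the clinical team which applies. The baseline wording needs no change.

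**Cost:** one short question for those positive on item 9 (none extra with the combined item), a wording change in protocol and forms with IRB notification, and possibly a few more hand-offs.

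**If follow-up is complete,** which the partly past-tense SAP of September 2021 suggests may be so: check the stored forms for the wording used, state it in the report, and correct Appendix C before it is reused. That costs a form check and one sentence.

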I. STUDY IDENTIFICATION INFORMATION

TITLE OF PROTOCOL: Emergency Department Longitudinal Integrated Care 2.0 (ED-LINC 2.0)

PRINCIPAL INVESTIGATOR: [name] MD MS

FUNDER OF PROTOCOL: National Institute of Drug Abuse (NIDA)

CLINICALTRIALS.GOV: A description of this clinical trial will be available on <http://www.clinicaltrials.gov>, as required by U.S. Law. **NCT03699085**

SAP Version date: September 2021

Table of Contents:

Summary of Clinical Trial Features.....	Page 3
Primary Outcome Measures.....	Page 4
Refusal Rates	
Follow-up Completion Rates	
ED-LINC Intervention and usual Care process Outcomes	
Implementation Appropriateness	
Satisfaction	
Perception of Care Coordination	
Secondary Outcome Measures.....	Page 5
Substance Use	

Summary of Clinical Trial Features:

The *Emergency Department Longitudinal Integrated Care* (ED-LINC) intervention is a stepped collaborative care model of care initiated from the ED for patients with OUD that combines evidence-based treatment elements, proactive care coordination and population-level outcome tracking. ED-LINC builds upon previous work by tailoring the collaborative care model for patients at high risk for OUD presenting to the ED. A central objective of ED-LINC is to provide evidence-based treatment for OUD and related co-morbidity while in the ED in conjunction with proactive longitudinal care coordination that links patients to ongoing treatment. Weekly caseload supervision with measurement-based care outcome tracking allows for the stepping up of care for patients with recalcitrant symptoms, as well as opportunities to oversee care management linkages to community services targeting the key outcomes of initiation of MOUD and retention in MOUD treatment.

The main objective of this study was to conduct a pilot pragmatic randomized clinical trial of ED-LINC (n=20) compared to usual care (n=20) for ED patients at a single-site at high risk for OUD. The primary outcomes of this study pertain to feasibility of the model, research strategy and implementation.

Primary Outcome Measures

All primary outcome measures used **descriptive statistics**

Refusal Rate was calculated as the number of patients that refused or declined the self-report screening procedure in the ED divided by the eligible number of patients that could have done the self-report screening during the enrollment period.

Follow-up Completion Rates were calculated for each followup timepoint and were calculated as the number of participants that completed follow-up divided by the total number of participants randomized to each arm of the trial. The 6-month followup completion rate is shown as the number of participants that completed the 6-month self-report interview divided by the number of participants randomized to each arm.

ED-LINC Intervention and usual Care process Outcomes were determined from extensive research notes. Specifically the EDLINC interventionist conducted a process validity assessment and documented the number of unique ED-LINC elements completed for each participant in the intervention.

Implementation Appropriateness was calculated by providing this validated self-report measure to each participant randomized to the ED-LINC assessment. Results were dichotomized to calculate the frequency of participants who 'agreed' or 'completely agreed' that the intervention was 'applicable' and 'seemed like a good match' to document appropriateness.

Satisfaction was calculated using a validated satisfaction questionnaire and provided to all participants at six-months. Each participant will complete the questionnaire and their results will be summed. The median and IQR range will be calculated for participants in each group that complete the assessment.

Perception of Care Coordination will be done using questions from a validated scale. The Wilcoxon Rank Sum test will be used to determine if there are significant differences between groups.

Secondary Outcome Measures

Substance Use

Substance use will be measured using the timeline follow back procedure which is a validated calendar method to determine days of use in a certain calendar period. First, we will sum days of use of illicit opioid use in 30 days at baseline and each followup period for each participant. The mean days of use/30 days with an associated standard deviation will be calculated at each time-period for both the ED-LINC intervention and the usual care control groups.

Next, we will evaluate variance of the data and test model fit on unadjusted data using different distributions. Given previous work, we anticipate the data to be skewed and zero-inflated. Thus, we hypothesize that we may use a normal Gaussian, Poisson or negative binomial distribution.

Once model fit is determined, a reverse stepwise selection will be performed using a linear regression of clinician-selected input variables, alongside the intervention and TLFB timepoint, and an elimination threshold of $p > 0.05$

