- Patients with score of ≥ 4 on the NIDA modified ASSIST for illicit opioids (e.g. heroin) OR a score of ≥ 4 on the NIDA modified ASSIST for prescription opioids
- Currently have a phone
- Able to provide a phone number and one additional piece of contact information

b. Exclusion Criteria:

- They are incarcerated or under arrest
- Non-English speaking
- Live beyond a 50 mile radius of HMC
- Require active resuscitation in the ED or other clinical area at the time of RA approach
- Are receiving palliative care services or hospice care for a chronic illness such as metastatic cancer
- Are in the ED or hospital for a primary psychiatric emergency such as suicidal ideation or attempt

- Receiving chronic opioid therapy (COT) defined as prescription opioids for most days out of the last 90 days for a chronic pain condition
- In the ED for sexual assault

3. Recruitment and Retention Estimates

Estimates for the recruitment plan are based on literature related to feasibility studies. Specifically, the sample size of this pilot is related to the pragmatics of recruitment and a sample of n=30 for each group is related to the necessity for examining feasibility including rates of refusal for each group as well as retention in both arms.⁸ Previous work by the research team delivering collaborative care from the ED for patients with injury and prescription drug misuse (ED-LINC 1.0) described excellent recruitment and retention rates of > 80% over six months for subjects getting the intervention.⁹ Therefore the study intends to recruit at least 30 participants per arm with retention rates at each assessment and/or follow-up time point of 80%.

III. STUDY PROCEDURES

A. EMR pre-screen OR staff referral

The study team will be accessing and obtaining PHI from the HMC electronic medical record (EMR) to determine if patients have risk for opioid problems or opioid use disorder. Specifically, each morning a member of the study team will review the current census of patients in the ED and first determine if they are eligible based on criteria listed above easily obtainable (e.g. age, chief complaint) by looking at the track shell using FirstNet. Next, the study team member will look at the EMR for possible eligible participants to see if one of the following items exists in the EMR which are associated with an increased risk of opioid use disorder based on literature:

- Previous overdose
- Diagnosis of OUD in the problem list

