- Previous healthcare visit related to substance use
- Chief complaint for the current ED visit suggestive of injection drug use
 - Skin/soft tissue complaint
 - Request for detox or concern for withdrawal
 - Overdose
- Any EDIE criteria which includes:
 - 5 ED visits in 12 months
 - PMP criteria
 - More than three (3) prescribers within 12 months
 - More than 4 controlled substance II-V prescriptions within 12 months
 - More than 2 controlled substance II-V prescriptions within last 40 days
 - Any prescription for Methadone, Suboxone, fentanyl transdermal, LA morphine, and LA oxycodone within last 6 months
 - Any overlapping prescriptions for narcotics (controlled substance II-V) and benzodiazepines within last 6 months
 - More than 100 average MED/day prescribed within last 40 days
 - Care Plan
 - From HMC
 - From other hospital

- Patient Requiring Coordination (PRC) program

In addition to using the EMR pre-screen, the study team will take referrals from staff working with patients in the ED. Specifically, structured assessments are often provided to patients while in the ED and if a patient is known to be at-risk for OUD, the study team can be notified to perform further self-report screening (see below).

If the study team has approached all possible eligible patients in the ED based on EMR pre-screen criteria and have exhausted staff referrals for the time being, they can continue to approach possible eligible participants based on eligibility criteria listed in Section 2 with the self-report screening questions (e.g. universal screening).

B. Approach and verbal consent for verbal screen and additional eligibility criteria

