For daily study activities, a study team member will manually abstract EMR data into RedCap to determine eligibility. Later, to obtain clinical outcome data, the study will utilize a UW Medicine EMR data warehouse (Amalga) query to facilitate automated abstraction of information. The study team will work with the Department of Emergency Medicine clinical analyst to support this query who has undergone extensive GCP training and signed the confidentiality waiver for this study. The clinical analyst will conduct an Amalga query and data abstraction may occur through one of three delivery methods:

- A SQL Server Reporting Services (SSRS) Report hosted on a UW Medicine server
- An upload to a custom built REDCap project hosted by the UW ITHS
- A flat file delivered to the study team on a secured shared drive

Data from the automated Amalga query or manual chart review will be imported or entered into the enrollment log housed within REDCap or equivalent data capture method (e.g., Excel).

2. Patient Enrollment Log

The study team will document all patients that screen in or out of the study in an electronic log housed within REDCap or equivalent data capture method on a secure UW Medicine server (e.g., Excel). The enrollment log will contain a single form with variables abstracted from the EHR and PHI will only be obtained for patients that screen-in and provide informed consent. At the conclusion of the record retention period the form containing identifiers will be deleted from the enrollment log database, thus severing the link between participant identifying information and de-identified study data.

The enrollment log will also be used to track patient approach date and status (e.g., consented, refused, excluded); if the patient was excluded, the reason for exclusion (e.g., active psychosis); overall study status (e.g., active, completed, withdrawn); and randomization assignment (for those patients that screen in to the study and provide informed consent). This data will be obtained from the Harborview EMR, from interviewers' contact with patients, or from patient self-report and entered directly entered in to REDCap via secure login and password by a member of the

study team. The team is aware that at times, due to technical issues or lack of Wi-Fi access, the enrollment logging procedures may require the team to take alternative measures (e.g., computer/iPad or paper logging) for subsequent entry into REDCap.

3. Patient-Reported Outcomes (PRO)

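### As written, the primary refusal rate is divided by eligible patients rather than patients approached, so it understates refusal whenever some eligible patients were never asked

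*SAP*

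**What the plan says.** The SAP (Primary Outcome Measures, Refusal Rate) takes as numerator "the number of patients that refused or declined the self-report screening procedure in the ED". The denominator follows: "divided by the eligible number of patients that could have done the self-report screening during the enrollment period". It does not define eligible for this purpose and does not mention approach. The outcome is descriptive: "All primary outcome measures used descriptive statistics". No target, margin or expected value is given.

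The protocol describes how patients reach the screen. In section III.A, "each morning a member of the study team will review the current census of patients in the ED", followed by a check of the medical record for risk factors. Staff referrals are a second route. A third route, screening without a risk flag, opens under a condition that begins "If the study team has approached all possible eligible patients in the ED based on EMR pre-screen criteria and have exhausted staff referrals". Under section III.B, staff consult the care team if possible and judge mental status before introducing themselves. Section IV.A restricts approach by Glasgow Coma Scale score.

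The enrollment log (sections VI.B.2 and VII.B.1) records the date and outcome of each approach and follows status from the pre-screen onward. For that log, "PHI will only be obtained for patients that screen-in and provide informed consent". One of the pre-screen risk criteria in section III.A is "5 ED visits in 12 months".

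Section III.C describes a second refusal point, at written consent, and states that these refusals are tracked within the main feasibility outcome. The SAP formula does not include them.

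**The concern.** The numerator and denominator describe different groups. Refusers are by definition people who were asked, while the denominator is a pool of people who might have been asked. The pool cannot be the set that meets the full trial criteria, because those require an m-ASSIST score that the screen itself produces. It must be some earlier group, and the SAP does not say which.

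If eligible patients were missed for lack of staff or time, the literal formula counts each of them as someone who did not refuse. The reported rate then mixes two quantities that call for different responses. One is how acceptable the screen is to patients who are asked. The other is how much of the eligible pool the team managed to reach.

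This matters because refusal is the first primary outcome listed. Protocol section II.B.3 gives the examination of refusal rates as part of the reason for the sample size, and section II.A says that the study is meant to provide feasibility information for later ED-LINC studies. A rate that falls when staffing is thin could suggest good acceptability where the problem is reach.

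**Working it through.** The documents give no refusal count, approach count or expected rate, so there is no stated figure to reproduce. The check is algebra with assumed values.

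**Inputs.** Let E be eligible patients, A the eligible patients approached and D those who declined. Write r = D/A for refusal among those asked and a = A/E for the share approached. The form of D/E comes from the SAP. The values of r and a are assumptions.

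**Denominator effect.** Count each patient once and let A be a subset of E. Then

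SAP rate = D/E = (D/A) × (A/E) = r × a.

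This is below r whenever a < 1 (and r > 0) and equals r when a = 1.

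| r (assumed) | a = 1.0 | a = 0.8 | a = 0.6 | a = 0.4 |
|---|---|---|---|---|
| 20% | 20% | 16% | 12% | 8% |
| 30% | 30% | 24% | 18% | 12% |
| 50% | 50% | 40% | 30% | 20% |

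Two further values at r = 30%: 0.30 × 0.75 = 22.5% and 0.30 × 0.50 = 15%.

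The formula also cannot be inverted without a. A reported 15% fits r = 15% with everyone approached, r = 20% with 75% approached (0.20 × 0.75 = 0.15), or r = 30% with half approached.

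**Recruitment routes.** The identity needs every refuser to belong to E. Patients found by staff referral or by screening without a risk flag may fall outside a pool built from the record pre-screen. The SAP does not say whether they enter either part of the fraction.

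**Repeat visits.** Suppose 100 patients are approached once each and 30 decline, giving 30%. Now count log entries instead of patients, under three assumed patterns:

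- 10 refusers are approached and decline twice more: (30 + 20)/(100 + 20) = 50/120 = 42%.
- As above, and 20 patients who completed the screen but did not qualify are also screened twice more: (30 + 20)/(100 + 20 + 40) = 50/160 = 31%.
- Only those 20 screened-out patients return: 30/(100 + 40) = 30/140 = 21%.

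Repeat entries can therefore raise the rate, lower it or leave it nearly unchanged, depending on who returns. The documents contain nothing that settles this.

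**The case against.** The strongest reply is that the wording already excludes most patients who were not asked. Someone held back for mental status or by the care team could not have done the screen, and that reading is natural. Patients discharged before approach are arguably excluded too, and patients missed by the morning census may never have been assessed as eligible. The protocol also foresees times when everyone flagged by the pre-screen has been approached, and then the two denominators coincide. The analysts may in practice have divided by patients approached.

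Much of this stands. It shrinks the group at issue to patients who were flagged, able to take part and simply not reached. It does not remove them. The protocol treats complete approach as a condition that may or may not be met, and the SAP nowhere says approached. The wording is ambiguous, and for a primary outcome that is reason enough to state it.

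It is also fair that the outcome is descriptive, that no decision threshold depends on it, and that the log lets a reader be shown both denominators.

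Three stronger readings are tempting but unsupported.

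- A reader might infer that repeat visits by non-consenters cannot be recognised, because the log holds no identifiers for them. But protocol section III.A gives the team access to identifiable records at pre-screen, and section VI.B.1 has record data abstracted into REDCap to determine eligibility. The documents show only that no method or rule is stated.
- A reader might infer that repeats push the rate up. That holds only if repeat screen-outs are ignored.
- A reader might conclude that the outcome does not measure refusal at all. It still gives refusals as a share of the eligible pool, and it equals refusal among those asked when all are approached and each is counted once.

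**Conclusion.** The concern holds in a limited form. On its literal wording the primary refusal rate is r × a, so it understates refusal among those asked in proportion to the share of eligible patients not approached. At an assumed 30% refusal the shortfall is 7.5 percentage points at 75% approached and 15 points at 50%. It is zero if all were approached, or if the analysts already limited the denominator to patients approached. The true size cannot be known from the documents, because they report neither r nor a.

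Two gaps stand beside this. The counting unit and a repeat-visit rule are missing, although frequent ED use is one of the selection criteria; no direction of bias can be claimed from that. Refusal at written consent, which the protocol places in the main feasibility outcome, is absent from the SAP rate. The definition should be corrected for reporting. None of this undermines the trial.

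**What to change.** Amend the SAP definition and re-tabulate:

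1. **Refusal rate:** patients who declined the self-report screen divided by patients approached and invited to do it, taken from the approach status in the log.
2. **Reach:** patients approached divided by pre-screen-eligible patients, reported separately. Limit the numerator to patients found through the pre-screen, and show staff referrals and screening without a risk flag on their own lines, so that the ratio has one defined pool.
3. **Counting unit:** count first approaches where repeats can be identified. Otherwise label the unit as approaches rather than patients, and make no statement about the direction of any repeat-visit bias.
4. **Consent-stage refusal:** patients who declined written consent divided by eligible patients offered it, with the reasons that protocol section III.C already collects.
5. **Precision:** exact 95% confidence intervals for each proportion. If the unit is approaches, note that the interval treats repeat approaches to one person as independent.

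The SAP is dated September 2021 and describes the refusal calculation in the past tense, so the remedy should rely on data already logged rather than on new fields. The cost is a few lines of SAP text and a re-tabulation. The downside is that the stated refusal rate may look less favourable.
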